If at any point during the trial $\Pr(\mu_i > \max(u_j \text{ for all } j \neq i) | \text{data}) > 0.975$ (< 0.025), the trial will be terminated and treatment i will be selected as superior (inferior). If the maximum accrual is reached and $\Pr(\mu_i > \max\{u_j \text{ for all } j \neq i\} | \text{data}) > 0.8$ (< 0.2), treatment i will be selected as superior (inferior). A treatment arm will be dropped at any point during the trial if $\Pr(\mu_i > 12 | \text{data}) < 0.1$, for $i=1,2,3,4$. Table 6 given below summarizes operating characteristics of the design. The historical median EFS is 12 months. The tables below assume an accrual rate of 4 patients per month. The trial will be stopped early and a treatment selected as being “better” if the probability that one treatment’s median EFS is larger than the other’s EFS exceeds 0.975. If the trial does not stop early and the maximum 120 patients are accrued, a treatment is selected as being “better” if the probability that one treatment’s median EFS is larger than the other’s EFS exceeds 0.8. A treatment arm will be dropped at any point during the trial if the probability that the treatment’s median EFS is larger than 12 months is less than 0.1. The “# of patients treated” row is the average number of patients treated on a given arm under the given scenario. When the medians all equal to 12 months (scenario 1), the probability of selecting one of the three arms (i.e., a false positive result) is at most 3.7 %. The probability of selecting the best treatment (i.e., a true positive result) for scenario 5, when the medians TTP are 12, 12, and 24 months for the arms, respectively, are 0.1%, 0.04%, 0.2%, and 79.7%.

Table 6: simulation results (simulation=5000) for transfusion dependent patients with the minimum randomization probability set as 0.1 and tuning parameter as 0.5

			treatment		
		BSC	DAC	AZA3	AZA5
1	True Median EFS	12	12	12	12
	# of patients treated	29	28.9	28.8	28.6

	Pr(selected)	0.037	0.036	0.034	0.029
	Pr(selected early)	0.001	0.001	0.001	0.0004
	Pr (stopped early)	0.235	0.233	0.253	0.244
2	True Median EFS	7	7	7	7
	# of patients treated	14.2	14.3	14.3	14.4
	Pr(selected)	0.029	0.024	0.027	0.027
	Pr(selected early)	0.0002	0	0.0002	0.0002
	Pr (stopped early)	0.764	0.774	0.773	0.755
3	True Median EFS	7	12	15	20
	# of patients treated	13.2	24.2	32.3	42
	Pr(selected)	0	0.003	0.035	0.496
	Pr(selected early)	0	0.0004	0.003	0.036
	Pr (stopped early)	0.971	0.58	0.296	0.032
4	True Median EFS	12	12	12	20
	# of patients treated	24	24.3	23.8	40.7
	Pr(selected)	0.003	0.004	0.006	0.572
	Pr(selected early)	0	0.0002	0.0002	0.027
	Pr (stopped early)	0.538	0.533	0.544	0.014
5	True Median EFS	12	12	12	24
	# of patients treated	22.3	22.3	22	42.5
	Pr(selected)	0.001	0.0004	0.002	0.797
	Pr(selected early)	0	0.0002	0	0.059
	Pr (stopped early)	0.713	0.719	0.721	0.006

The design software adaptive Randomization version 4.1.1. developed by the Department of Biostatistics at M. D. Anderson Cancer Center (MDACC) was used to generate the OC table.

Toxicity Monitoring

Evidence of Toxicity will be monitored closely for all patients except for the patients under the BSC. With 10 patients fairly randomized to each arm of the four arms, there will be at most 80 patients being adaptively assigned to any arm. Taking the initial 10 patients assigning to each arm, the maximum number of patient per treatment arm will be 90. For each treatment, treatment will be terminated if $\Pr(\theta_E > 0.2 | \text{data}) > 0.88$. where θ_E is the proportion of any grade 3 or greater treatment related non-hematologic toxicities attributed to study drug and is assumed to follow a non-informative prior of Beta (0.4, 1.6) That is, the trial will be terminated if at any time during the study, there is a more than 88% chance that the average rate of grade 3 or greater treatment related

non-hematologic toxicity is more than 20%. Patients will be monitored by a cohort size of 10 according to the following stopping boundaries for toxicity. The design software Multc Lean Desktop (version 2.1) developed by the Department of Biostatistics at M. D. Anderson Cancer Center (MDACC) was used to generate the futility/toxicity stopping boundaries and the OC table.

Table 7: stopping boundaries for toxicity

Number of patients evaluated	Stop the trial if there are this many treatment related toxicities
10	4-10
20	7-20
30	9-30
40	12-40
50	14-50
60	17-60
70	19-70
80	21-80

Table 8: Operating characteristics of safety monitoring

True Toxicity Rate	Prob (stop the trial early)
0.15	0.08
0.2	0.28
0.25	0.62
0.3	0.88

Analysis Plan

Data analysis will be performed using SAS or S-plus, as appropriate. All patients will be included in the intent-to-treat analysis for efficacy. Demographic and disease characteristics of the patients at registration will be summarized using descriptive statistics such as mean, standard deviation (SD), median and range. The EFS under different treatment will be estimated by Kaplan-Merier method, along with the 95% credible intervals, and logrank test will be used to assess the EFS differences under different treatments. The Cox proportional hazards model will be used to analyze the effects of treatments and other covariates.

Figure 1. Survival of Patients with Low Risk MDS According to the Lower Risk Prognostic Model

[figure not shown]

Table 9. Prognostic Model of Lower-Risk Myelodysplastic Syndrome: Multivariate Analysis Poor-Prognosis Parameters and Assigned Score

Adverse Factor *P* Assigned Score

Unfavorable cytogenetics < .001 1

Age \geq 60 years < .001 2

Adverse Factor	P	Assigned Score
Hgb < 10 g/dL	< .001	1
Plt, $\times 10^9/L$		
< 50	< .001	2
50-200	< .001	1
BM blasts $\geq 4\%$	< .001	1

Table 10. Prognostic Model of Lower-Risk Myelodysplastic Syndrome: Estimated Survival Outcome Within Each Score Range

Score	No. of Patients	Median Survival (months)	4-Year Survival Rate (%)
0	11	NR	78

Score No. of Patients Median Survival (months) 4-Year Survival Rate (%)

1	58	83	82
2	113	51	51
3	185	36	40
4	223	22	27
5	166	14	9
6	86	16	7
7	13	9	NA

XI. References:

1. Nimer SD (2008) Myelodysplastic syndromes. *Blood* 111:4841–4851.

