Phase II Randomized Study of Lower Doses of Decitabine (DAC; 20 mg/m² IV daily for 3 days every month) versus Azacitidine (AZA; 75 mg/m² SC/IV daily for 3 days every month) versus Azacitidine (AZA; 75 mg/m² SC/IV daily for 5 days every month) in MDS Patients with Low and Intermediate-1 Risk Disease Transfusion-Dependent versus Best Supportive Care (BSC) in MDS Patients with Low and Intermediate-1 Risk Disease Transfusion-Independent

Study Chair

[name]
The University of Texas M.D. Anderson Cancer Center
[name]
[name]
[contact]
[contact]

Co-Chair

[name]
The University of Texas M.D. Anderson Cancer Center
[name]
[name]
[contact]
[contact]
[contact]

I. OBJECTIVES

Primary:

Compare the event-free survival rates of two different drugs: DAC versus AZA on an abbreviated schedule to a standard arm of AZA given over 5 days in patients with low-risk MDS transfusion-dependent and to BSC in patients with low-risk MDS transfusion-independent.

Secondary:

Compare the response rates for the transfusion independent and the transfusion dependent patients. For example the response rate of two different drugs DAC versus AZA on abbreviated schedule to a standard arm of AZA given over 5 days.

Evaluate the durability of response, the overall and transformation-free survival rates, and the safety profile of 2 different drugs.

The quality of life protocol (2014-0636) titled “Interventional Validation of an MDS-Specific Measure of Quality of Life: Assessing the Responsiveness of the QUALMS-1 to Different Hypomethylating Agent Regimens for Low and Intermediate Risk Disease” was written specifically as a companion study to protocol 2014-0112 and may be offered as an optional assessment to patients enrolled onto this protocol.

II. RATIONALE

Myelodysplastic syndromes (MDS) are clonal hematopoietic stem-cell disorders characterized by ineffective hematopoiesis, peripheral-blood cytopenias, and increased tendency to progress to acute myeloid leukemia (AML).¹ Median age of patients with MDS is approximately 70 years.² This patient population is frequently affected by other comorbid conditions, a factor that often influences treatment decisions.

Treatment of MDS is based on prognostic factors that predict survival and progression to AML. The most widely used prognostic system for therapeutic decision making is still

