is negligible (<1%), interactions due to displacement of more highly protein bound drugs from plasma proteins are not expected.

Decitabine has been approved by the Food and Drug Administration (FDA) in the United States for treatment of patients with MDS including previously treated and untreated, *de novo* and secondary MDS of all French-American-British subtypes (refractory anemia, refractory anemia with ringed sideroblasts, refractory anemia with excess blasts, refractory anemia with excess blasts in transformation, and chronic myelomonocytic leukemia) and intermediate-1, intermediate-2, and high-risk International Prognostic Scoring System (IPSS) groups.

The major toxicity is myelosuppression. Decitabine may also cause fever, cough, constipation, diarrhea, nausea, vomiting, edema, headache, insomnia and hyperglycemia. Rarely, decitabine can cause allergic reactions.⁴

B. Azacitidine (AZA)

Azacitidine, a ring analog of the pyrimidine nucleoside cytidine, has effects on cell differentiation, gene expression, and DNA synthesis and metabolism. Since the early 1970s, azacitidine has been investigated in the US for the treatment of acute leukemia. Clinical trials have focused primarily on patients with disease refractory to conventional chemotherapy. These investigations indicated azacitidine has activity in the treatment of acute myelogenous leukemia (AML). Clinical trials subsequently have been conducted to evaluate the effects of azacitidine in a variety of other malignant and hematologic

disorders, including solid tumors, hemoglobinopathies (thalassemia and sickle cell anemia), and myelodysplastic syndromes (MDS).

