In 1985, the Cancer and Leukemia Group B (CALGB) study investigators began clinical trials with azacitidine in MDS patients under the auspices of the National Cancer Institute (NCI). Results from the three studies conducted by the CALGB (Protocols 8421, 8921, and 9221) have been published. The first two CALGB studies (Protocol 8421 and Protocol 8921) were uncontrolled Phase 2 investigations. The most recent CALGB study (Protocol 9221) was a Phase 3 investigation that compared azacitidine to supportive care alone. The azacitidine dose investigated in the CALGB studies was 75 mg/m²/day for 7 days, repeated on a 28-day cycle. Azacitidine was administered by continuous IV infusion in the first study (Protocol 8421), and by SC injection in the two studies that followed. The dose was adjusted based on toxicity and clinical response. In the Phase 3 investigation (Protocol 9221), azacitidine produced higher response rates than supportive care alone. In addition, azacitidine prolonged the time to transformation to AML or death.

The efficacy of azacitidine to treat MDS also was evaluated in 7 open-label studies conducted outside the CALGB protocols. The dosage regimen used in 6 of these studies was 75 mg/m² given daily for 7 days every 3-4 weeks by SC injection in 4 studies, SC or IV in 1 study, and the route was not specified in the last study. The dosage regimen used in the seventh study was 5-35 mg/m²/day given by continuous IV infusion for 14 days. The lowest response rate was found in this seventh study, which

suggests the mechanism of 5-azacitidine's activity requires repeated administration of a minimally effective dose to achieve improvement in hematologic parameters.

As with other antimetabolites, bone marrow suppression (leukopenia, thrombocytopenia) is a common adverse event associated with azacitidine. However, myelosuppression generally occurs more often and with greater severity at doses higher than those used to treat MDS. Gastrointestinal toxicity (ie, nausea, vomiting, and diarrhea) can limit the dose of azacitidine in any patient population. Infrequent adverse effects include neuromuscular aches, generalized weakness, renal tubular acidosis, and liver enzyme abnormalities. Erythema and burning at the injection site can occur following SC administration, which usually resolves within 24-72 hours.

Azacitidine is approved for all patients with MDS using FAB criteria (up to 30% blasts).

IV. Eligibility criteria

Inclusion criteria:

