Patients may receive their second course of therapy without interruption, regardless of their degree of myelosuppression. After the first course of therapy, the interval between subsequent cycles of therapy could be shortened or prolonged at the discretion of the investigator. Subsequent cycles can be given prior to peripheral blood count recovery if considered to be in the best interest for the patient and after discussion with the principal investigator and the discussion documented in the patient's medical record. If study drug related prolonged myelosuppression (≥ 42 days of absolute neutrophil count [ANC] $< 1 \times 10^9/L$ and platelet count $< 30 \times 10^9/L$) is observed after cycle 2, subsequent cycles may be given at the next lower dose (DAC, 15 mg/m²/day, then 10 mg/m²/day, then 5 mg/m²/day; AZA, 56 mg/m²/day, then 37 mg/m²/day, then 18 mg/m²/day) after recovery (ANC $\geq 1 \times 10^9/L$ and platelet count $> 50 \times 10^9/L$) and subsequent cycles of

AZA. Granulocyte-colony stimulating factor for fever of unknown origin, infection, and/or ANC $<0.75 \times 10^9/L$ can be administered.

Dose reductions can also be made in other clinical situations where this step is considered to be in the best interest for the patient and after discussion with the principal investigator and the discussion documented in the patient's medical record. The following table is a suggestion for dose modifications in subsequent treatment courses:

Table 1: Dose levels adjustment

Dose level	AZA (mg/m ²)	DAC (mg/m ²)
-1	56	15
-2	37	10
-3	18	5

VI. BASELINE AND PER-TREATMENT EVALUATION

Baseline

1. A complete history and physical examination within 14 days prior to study entry.
2. CBC, differential platelet count.
3. Creatinine, bilirubin, ALT or AST,
4. Bone marrow aspirate and/or biopsy with cytogenetics (if bone marrow not done within 6 weeks and cytogenetics (if previously abnormal) within 3 months prior to study entry.

5. Serum or urine pregnancy test within 7 days of treatment start for women of childbearing potential
6. Documentation of frequency of transfusions (PRBC and Platelets) prior to start of each cycle
7. Documentation of any prior administration of growth factors and ESA

Prestudy laboratory tests must be obtained within 14 days of registration.

During therapy

1. CBC, differential, and platelet count once monthly prior to start of each cycle
(the differential may be omitted when the WBC is $< 0.5 \times 10^9/L$)

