	Pr (stopped early)	0.806	0.814	0.028
3	True Median EFS	3	3	3
	# of patients treated	10.5	10.5	10.5
	Pr(selected)	0.046	0.043	0.045
	Pr(selected early)	0.001	0.001	0.001
	Pr (stopped early)	0.779	0.779	0.777
4	True Median EFS	7	9	14
	# of patients treated	23.6	36.2	57.4
	Pr(selected)	0.003	0.013	0.882
	Pr(selected early)	0.0002	0.003	0.217
	Pr (stopped early)	0.921	0.686	0.0162
5	True Median EFS	7	12	12
	# of patients treated	23.1	56.6	55.6
	Pr(selected)	0.001	0.242	0.235
	Pr(selected early)	0.0002	0.04	0.036
	Pr (stopped early)	0.877	0.12	0.13

6	True Median EFS	4	7	12
	# of patients treated	13.3	29.5	45.3
	Pr(selected)	0.001	0.014	0.883
	Pr(selected early)	0	0.002	0.357
	Pr (stopped early)	0.994	0.866	0.036
7	True Median EFS	4	7	10
	# of patients treated	13.9	34.1	48.1
	Pr(selected)	0.001	0.039	0.757
	Pr(selected early)	0	0.004	0.194
	Pr (stopped early)	0.987	0.661	0.083

Toxicity Monitoring

Evidence of toxicity will be monitored closely for all patients. As expected, there will be 150 transfusion-dependent patients enrolled which includes the 120 patients initially recruited and another 30 patients who have changed from transfusion independence to dependence. With 10 patients fairly randomized to each arm, there will be at most 120 patients being adaptively assigned to any of the three arms. Taking the initial 10 patients assigning to each arm, the maximum number of patient per treatment arm will be 130. For each treatment, treatment will be terminated if $\Pr(\theta_E > 0.2 | \text{data}) > 0.9$, where θ_E is the proportion of any grade 3 or higher treatment related non-hematologic toxicities. It is assumed to follow a non-informative prior of Beta (0.4, 1.6) That is, the trial will be terminated if at any time during the study, there is a more than 90% chance that the average rate of grade 3 or greater treatment related non-hematologic toxicity is more than 20%. Patients will be monitored by a cohort size of 10 according to the following stopping boundaries for toxicity. The design software Multc Lean Desktop (version 2.1) developed by the Department of Biostatistics at M. D. Anderson Cancer

Center (MDACC) was used to generate the futility/toxicity stopping boundaries and the OC table.

Table 4: stopping boundaries for toxicity

Number of patients evaluated	Stop the trial if there are this many treatment related toxicities
10	5-10
20	7-20
30	10-30
40	12-40
50	15-50
60	17-60
70	19-70
80	21-80
90	24-90
100	26-100
110	28-110
120	30-120

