Appendix A

Appendix Subtitle:

Leukemia-specific Adverse Event Recording and Reporting Guidelines

These guidelines serve to bring the Department of Leukemia in compliance with the institutional policy on Reporting of Serious Adverse Events-definition of expected AE- "All clinical protocols should include a list of the expected and anticipated events or hospitalizations relating to the study treatment" and Guideline for Good Clinical Practice 4.11.1 "All serious adverse events (SAEs) should be reported immediately to the sponsor except for those SAEs that the protocol or other document (e.g., Investigator's Brochure) identifies as not needing immediate reporting".

Adverse event is any untoward medical occurrence that may present during treatment with a pharmaceutical product but which does not necessarily have a causal relationship with this treatment.

Adverse drug reaction is a response to a drug which is noxious and unintended and which occurs at doses normally used in man for prophylaxis, diagnosis, or therapy of disease or for the modification of physiologic function.

Assessing causal connections between agents and disease is fundamental to the understanding of adverse drug reactions. In general, a drug may be considered a contributory cause of an adverse event if, had the drug not been administered, 1) the event would not have happened at all, 2) the event would have occurred later than it actually did, or 3) the event would have been less severe.

Adverse Events (AEs) will be evaluated according to current CTC version in each protocol. Only unexpected AEs will be recorded in the Case Report Form (CRF).

Expected events during leukemia therapy are:

1. *Myelosuppression related events (due to disease or leukemia therapy)*
 - a. *febrile or infection episodes not requiring management in the intensive care unit*
 - b. *epistaxis or bleeding except for catastrophic CNS or pulmonary hemorrhage*
 - c. *anemia, neutropenia, lymphopenia, thrombocytopenia, leukopenia, leukocytosis*
2. *Disease related events*
 - a. *symptoms associated with anemia*
 - i. *fatigue*
 - ii. *weakness*
 - iii. *shortness of breath*
 - b. *electrolyte abnormalities (sodium, potassium, bicarbonate, CO₂, magnesium)*
 - c. *chemistry abnormalities (LDH, phosphorus, calcium, BUN, protein, albumin, uric acid, alkaline phosphatase, glucose)*
 - d. *coagulation abnormalities*
 - e. *disease specific therapy (induction, maintenance, salvage, or stem cell therapy)*

- f. alopecia

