 - g. bone, joint, or muscle pain
 - h. liver function test abnormalities associated with infection or disease progression
 - i. disease progression
- 3. General therapy related events
 - a. catheter related events
 - b. renal failure related to tumor lysis syndrome or antibiotic/antifungal therapy
 - c. rash related to antibiotic use
- 4. **Hospitalization for the management of any of the above expected events**

Abnormal hematologic values will not be recorded on the CRF. For abnormal chemical values grade 3 or 4, the apotheosis will be reported per course in the CRF.

Serious Adverse Event Reporting (SAE)

A serious adverse event (experience) or reaction is any untoward medical occurrence that at any dose

- Results in death
- Is life-threatening
- Requires inpatient hospitalization or prolongation of existing hospitalization
- Results in persistent or significant disability/incapacity
- A congenital anomaly/birth defect.

Important medical events that may not result in death, be life-threatening, or require hospitalization may be considered a serious adverse drug experience when, based upon appropriate medical judgment, they may jeopardize the patient or subject and may require medical or surgical intervention to prevent one of the outcomes listed in this definition. Examples of such medical events include allergic bronchospasm requiring intensive treatment in an emergency room or at home, blood dyscrasias or convulsions that do not result in inpatient hospitalization, or the development of drug dependency or drug abuse (21 CFR 312.32).

(Sections relating to ORERM are for MDACC held IND studies only.)

Important medical events as defined above may also be considered serious adverse events. Any important medical event can and should be reported to the IRB as an SAE if deemed appropriate by the Principal Investigator, the IND Sponsor, or the Office of Research Education and Regulatory Management (ORERM).

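### Appendix A keeps hematologic toxicity out of the CRF adverse-event data, so the planned safety data cannot compare the arms on myelosuppression

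*Combined protocol and SAP*

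**What the plan says.** Section I lists among the secondary aims "Evaluate the durability of response, the overall and transformation-free survival rates, and the safety profile of 2 different drugs". Section VII repeats safety profile as the last secondary endpoint, without defining it.

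Section III says of decitabine "The major toxicity is myelosuppression", and of azacitidine that "bone marrow suppression (leukopenia, thrombocytopenia) is a common adverse event associated with azacitidine".

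Section IX sends the recording of all adverse events to Appendix A. Section VI (During therapy, item 6) does the same for CRF entry at the lead center and refers participating institutions to Appendix G. Appendix A states "Only unexpected AEs will be recorded in the Case Report Form (CRF" and then lists the expected events. The list includes neutropenia, thrombocytopenia and the other cytopenias with no grade limit, fever or infection handled outside intensive care, and bleeding short of a catastrophic CNS or lung hemorrhage. It closes the list with "Abnormal hematologic values will not be recorded on the CRF".

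Section VI requires "CBC, differential, and platelet count once monthly prior to start of each cycle". In Section XII, Part I, the stopping rule is built on the "proportion of any grade 3 or higher treatment related non-hematologic toxicities"; Part II uses the same kind of event. The Analysis Plan covers baseline description, EFS by Kaplan-Meier and logrank, and a Cox model. It says nothing about safety.

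**The concern.** The trial compares a short with a longer azacitidine schedule, a second drug on a short schedule and, in transfusion-independent patients, active treatment with supportive care alone. A reader choosing among these arms needs to know what each does to blood counts and what follows clinically. The protocol itself names this harm for both drugs, yet its recording rule takes the harm out of the adverse-event dataset. An arm could be selected on EFS and reported with a safety table that leaves out its principal toxicity. This matters most in Part II, where the alternative is no hypomethylating agent at all.

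**Working it through.** **Following hematologic harm through the plan**

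1. *Aim.* Sections I and VII make safety a secondary objective and endpoint.
2. *Named harm.* Section III: major for decitabine, common for azacitidine. Decitabine is given for 3 days only, so the 3-day versus 5-day contrast lies within azacitidine and rests on the second statement.
3. *Measured?* Yes: a CBC about once a month, before each cycle.
4. *Entered on the CRF as an adverse event?* No, at the lead center. Cytopenias and their usual clinical consequences are on the expected list, and abnormal hematologic values are excluded separately. Appendix A does provide for some CRF reporting of grade 3 or 4 chemistry abnormalities, so the treatment of blood counts differs from that of chemistry.
5. *Monitored by rule?* No. With the Beta(0.4, 1.6) prior and cutoffs of 0.90 (Part I) and 0.88 (Part II), all 12 boundaries in Table 4 and all 8 in Table 7 reproduce exactly. The boundaries are right for what they count, but by definition they do not respond to myelosuppression.
6. *Analyzed?* No safety summary by arm is specified from any source.

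**What a comparison could show if the data were kept**

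The sample sizes are the average allocations when all medians are equal. Table 3, scenario 1, gives 40.1, 40.6 and 40.5, so about 40 per arm. Table 6, scenario 1, gives 28.6 to 29, so about 29 per arm. The documents give no rates of grade 3-4 neutropenia. I assume 30% on one schedule and 50% or 55% on the other.

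Two-sided 5% test, pooled variance under the null, with p̄ the mean of p₁ and p₂:

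Power = Φ{ [(p₂ − p₁) − 1.96·√(2p̄(1−p̄)/n)] / √([p₁(1−p₁) + p₂(1−p₂)]/n) }

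- n = 40, 30% v 50%: (0.20 − 1.96 × 0.1095)/0.1072 = −0.137; power 0.45.
- n = 40, 30% v 55%: (0.25 − 1.96 × 0.1105)/0.1069 = 0.312; power 0.62.
- n = 29, 30% v 50%: (0.20 − 1.96 × 0.1287)/0.1259 = −0.414; power 0.34.
- n = 29, 30% v 55%: (0.25 − 1.96 × 0.1298)/0.1256 = −0.035; power 0.49.

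These treat the arms as fixed and equal in size, which adaptive allocation will not deliver exactly. They show that the comparison would be mainly descriptive, though a large difference could be seen. The gap in the plan does not depend on them.

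**The case against.** The strongest reply is that hematologic harm is not lost. Under Appendix A, serious events are reported whether expected or not, life-threatening and fatal ones within 24 hours. Hospitalizations for expected events enter the SAE log and annual report. Infection needing intensive care and catastrophic CNS or lung hemorrhage are outside the expected list, so the CRF should carry them. Section VI requires chart documentation of related grade 3 or higher events, and of transfusions and growth factors, before each cycle. A DSMB monitors safety, and stopping therapy for side effects is an EFS event. All of this stands. A reader might infer that the trial will hold no information on myelosuppression; the documents do not support that. What they show is that these sources are partial and that no planned analysis draws on them.

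A reader might also take the Appendix A sentence to bar the hemoglobin, platelet and neutrophil values used to score response. That strains it. The sentence sits in an adverse-event guideline beside the rule for chemistry abnormalities, and Section VIII has responses verified in the local medical record.

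Nor is a stopping rule limited to non-hematologic toxicity a fault in itself. In a disease defined by cytopenias it is a defensible choice.

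Finally, the documents do not establish that myelosuppression differs between 3 and 5 days of azacitidine. Section III says it is more frequent and more severe at doses above those used in MDS. That the arms differ is a question for the trial, and the reason to keep the data.

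**Conclusion.** The point holds for the CRF adverse-event data as planned. They cannot support a comparison by arm of hematologic harm, although the protocol names that harm for both drugs and makes safety a secondary endpoint. It should be corrected, but it does not threaten the primary analysis. The conclusion covers the lead center only: Appendix G and the Data Quality Management Plan, which apply to participating institutions, are not in the supplied text and cannot be checked. With the data kept, power would be about 0.45 to 0.62 in Part I and 0.34 to 0.49 in Part II under the assumed rates, so the gain is an honest description of the main toxicity rather than a firm test.

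**What to change.** - In Appendix A, for this protocol, limit the sentence on hematologic values to separate adverse-event entries for laboratory results.
- In Section VI and Appendix A, require CRF entry of hemoglobin, ANC and platelets, with value and date, from each scheduled CBC.
- Require CRF entry of grade 3 or higher infection, febrile neutropenia and bleeding, although these are classed as expected.
- In the Analysis Plan, report by arm within each Part the worst pre-cycle ANC and platelet grade relative to baseline, those clinical events, and the transfusion and growth-factor use already documented.
- State two limits: monthly pre-cycle counts can miss mid-cycle nadirs, and the count comparison with supportive care depends on those patients having the same monthly CBC. The present schedule is tied to treatment cycles.
- Confirm that the CRF rules for participating institutions agree.

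Leave the stopping boundaries unchanged. The cost is more CRF entry, mostly of results already obtained, one extra table and a wording change.
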